# STUDY OUTLINE

Study Title:	A Prospective, Multicenter, Randomized Comparison of the HydrusTM Aqueous Implant to the iStent for Lowering Intraocular Pressure in Glaucoma Subjects Undergoing Cataract Surgery (HYDRUS III Trial)					
Study Device:	The CE-marked HydrusTM Aqueous Implant (Ivantis, Inc., Irvine CA)					
Control Device:	The iStent Trabecular Micro Bypass (Glaukos Inc., Laguna Hills, CA) a CE-marked device for the study indication.					
Study Population:	Subjects with mild to moderate Primary Open Angle Glaucoma (POAG), pseudoexfoliative glaucoma, or pigmentary glaucoma undergoing cataract surgery.					
Study Objective:	Compare the effectiveness of the HydrusTM Aqueous Implant to the iStent for lowering intraocular pressure in glaucoma subjects undergoing cataract removal and intraocular lens implantation in the indicated study population.					
Study Design And Methods:	A post-market, prospective, multicenter, randomized clinical trial i which potential study participants with a positive diagnosis of POAG, pseudoexfoliative glaucoma, or pigmentary glaucoma and cataract will be screened for eligibility. If eligible criteria are met, the study participants will undergo a screening washout phase during which all glaucoma medications (topical and oral) will be discontinued.					
	Following wash-out, the subjects will return and be evaluated for a fully-washed-out baseline diurnal intraocular pressure (IOP). If the baseline IOP criterion is met, the subjects will be scheduled for cataract surgery and Intraocular Lens (IOL) placement.					
	After successful cataract extraction and IOL placement, subjects will be randomized to receive either a single HydrusTM Aqueous Implant or iStent .					
	Interim follow up visits will be conducted at 1, 7, and 30 days, and then at 3, 6, 12, 18 and 24 months where each subject's IOP will be measured and ocular health will be evaluated. The primary endpoint will be diurnal IOP at 12 months as measured by Goldmann tonometry, after wash out of any hypotensive glaucoma medications. There will be a visit at Month 18 and the final study visit will occur at 24 months.					

Number of Sites:	Up to eight clinical sites in Europe and one in South America.						
Selection Criteria:	Ocular criteria relates to the study eye only.						
	Inclusion Criteria:						
	• Male and female subjects, from 21 to 84 years of age.						
	• A diagnosis of primary open angle glaucoma (POAG),						
	pseudoexfoliative glaucoma (PXG), or pigmentary						
	dispersion glaucoma (PDG).						
	• An operable age-related cataract with BCVA of 20/40 or						
	worse, engible for phacoemuismcation.						

Protocol #: CP-10-002, Rev. C July 22, 2013

Exclusion Criteria:

Excluded from the study will be individuals with the following characteristics. Unless specified otherwise, all ocular criteria refer to the study eye only.

- Closed angle forms of glaucoma
- Diagnosis of acute angle closure, traumatic, congenital, malignant, uveitis, or neovascular glaucoma.
- Secondary (such as neovascular, uveitic, traumatic, steroid induced, lens induced, or glaucoma associated with increased episcleral venuous pressure), congenital, or developmental glaucoma.
- Previous argon laser trabeculoplasty (ALT). Selective laser trabeculoplasty (SLT) is allowed.

Primary Endpoint:	The primary effectiveness endpoint for this study is diurnal IOP at 12 months following the wash-out of all glaucoma medications.					
Secondary Endpoints:	Secondary effectiveness endpoints include					
	
 
A reduction in IOP of at least 20% following the wash-out, as compared to the washed-out baseline.
 
An IOP of no less than 5 mm Hg and no more than 18 mmHg at 12 months post washout.
 
					
Safety Endpoints:	Safety outcomes include loss of lines of BCVA, results of slit lamp and fundus examination, and the incidence of complications and adverse events.					
Statistical Analysis:	Descriptive statistics will be used to summarize subject demographic, procedural, and safety data. Secondary endpoints will be evaluated using tests of proportion for subjects meeting the specified endpoints.					

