# 5.0 STUDY ENDPOINTS

The primary effectiveness endpoint for this study is diurnal IOP at 12 months following the washout of all glaucoma medications.

Secondary effectiveness endpoints include:

- A reduction in IOP of at least 20% following the wash-out, as compared to the washed-out baseline.
- An IOP of no less than 5mmHg and no more than 18mmHg at 12 months post washout.

Safety outcomes include loss of lines of BCVA, results of slit lamp and fundus examination, and the incidence of complications and adverse events.

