# 8.2 Cataract Extraction and IOL Replacement

If the subject meets all criteria at the Baseline visit, he or she will be scheduled for surgery within 60 days of completing the Baseline visit. In the period between the baseline visit and the surgery date, the patient may be re-started on hypotensive medications after determination of the washed out diurnal IOP. Cataract replacement surgery will be done with phacoemulsification using standard techniques. IOL's suitable for glaucoma subjects will be selected according to physician or subject preference.

If the subject meets all intraoperative eligibility criteria, randomization to either the *Hydrus* group or *iStent* group will be performed at the end of the cataract extraction and IOL implantation. Computer-generated randomization lists will be used, with separate randomization lists for each clinical site. The site will open the randomization envelope upon completion of an uncomplicated cataract extraction and IOL implantation. The subject will not be informed of the randomization assignment and all study personnel will be instructed to maintain the "masking" of the treatment assignments.

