# Baseline

The Baseline visit is performed following glaucoma medication wash-out, to confirm subject eligibility after medications are discontinued. The following information will be captured at this visit:

- Bilateral assessment of any changes in ocular medical history and medications
- Bilateral manifest refraction
- Bilateral ETDRS best-corrected visual acuity
- Bilateral slit lamp biomicroscopyNon-diurnal Goldmann tonometry, fellow eye only
- Diurnal Goldmann tonometry, study eye only, taken at 3 time points:
  - Time 1: 8:00 AM ( $\pm$  1 hour)
  - Time 2: 4 hours later ( $\pm 1$  hour) than Time 1
  - Time 3: 4 hours later ( $\pm 1$  hour) than Time 2.

Mean diurnal IOP will be computed from the three IOP time points. The mean diurnal IOP must be  $\ge 22$  and  $\le 36$  mmHg in order to qualify for the study.

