#### Operative

Surgery will be scheduled after the subject successfully completes the baseline exam, but not more than 60 days after the date of the baseline exam. In the period between the baseline visit and the surgery date, the patient may be re-started on hypotensive medications after determination of the washed out diurnal IOP.

The following information will be collected at this visit:

- Randomization assignment
- Type of anesthesia
- •
- Clock hour location of Hydrus insertion
- Viscoelastic used
- Surgical complications
- Intraoperative adverse events (AEs)

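### The test of proportions for the 5–18 mmHg responder endpoint leaves the washed-out baseline IOP unused; a baseline-adjusted risk difference could gain precision at almost no cost

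*Combined protocol and SAP*

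**What the plan says.** The only analysis stated for the two secondary effectiveness endpoints is in the Study Outline, under Statistical Analysis: "Secondary endpoints will be evaluated using tests of proportion for subjects meeting the specified endpoints". The public text of section 6 adds no covariate, effect measure or confidence interval for them.

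The endpoint at issue is in section 5.0: "An IOP of no less than 5mmHg and no more than 18mmHg at 12 months post washout". The other secondary endpoint, a reduction of at least 20% from washed-out baseline, has baseline in its definition.

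The Baseline visit in section 8.6 provides the covariate. For the study eye, "Mean diurnal IOP will be computed from the three IOP time points", and the value decides entry: "The mean diurnal IOP must be" between 22 and 36 mmHg. On timing, section 8.6 (Operative) states "Surgery will be scheduled after the subject successfully completes the baseline exam", and section 8.2 says that randomisation "will be performed at the end of the cataract extraction and IOL implantation".

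**The concern.** Baseline washed-out diurnal IOP uses the same tonometry and three-time-point schedule as the 12-month measurement from which the endpoint is derived. If it predicts the 12-month value, a test that ignores it gives a wider interval and less power than the same data allow. The sample size rests on the primary endpoint, so nothing in the public text secures power for this comparison. Error rates are not at stake.

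The point covers only the 5–18 mmHg endpoint. Nothing is claimed about the primary analysis, whose text is cut in the public version.

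**Working it through.** **The plan's own figure.** None is given for this endpoint. The 65 evaluable and 75 randomised per arm in section 6.2 relate to the primary endpoint. Their effect size, SD, alpha and power are not shown, so they cannot be reproduced, and they do not bear on this point.

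**1. Is the covariate legitimate?** The order is washout, Baseline visit, surgery up to 60 days later, then randomisation at the end of the cataract procedure. Baseline IOP is therefore fixed before allocation. As an entry criterion, it should be present for every randomised eye.

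**2. Inputs from the protocol.** About 150 randomised (section 4.0) or 70 (section 8.1); 1:1 allocation and 15% loss at 12 months (section 6.2); entry range 22–36 mmHg (section 8.6); up to nine sites (Study Outline). The figures 150 and 70 conflict and need reconciling, so both are shown.

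**3. Assumed, not in the documents.** Baseline normal with mean 25.5 and SD 3.5, cut to 22–36 mmHg; 12-month SD 3.5; control mean 18 mmHg; effect 0.5 SD (1.75 mmHg); nine equal sites; random loss; two-sided 5% test; correlation 0 to 0.5 among enrolled eyes.

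**4. Plain test by formula.** The lower limit of 5 mmHg is negligible here.

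- Responder rates: control Φ(0) = 0.500; test Φ(1.75/3.5) = Φ(0.5) = 0.691.
- Evaluable per arm: 150 × 0.85 / 2 = 63.75, about 64.
- SE = √[(0.500 × 0.500 + 0.691 × 0.309)/64] = 0.0851, so the 95% half-width is 1.96 × 0.0851 = 16.7 points.
- Pooled SE = √[2 × 0.5955 × 0.4045/64] = 0.0868.
- Power = Φ[(0.191 − 1.96 × 0.0868)/0.0851] = Φ(0.25), about 60%.
- With 70 randomised (about 30 evaluable per arm) the same formula gives about 32%.

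Simulation gives 59–62% and 32–34%, with an average half-width of 16.9 points at 150.

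**5. Plain against adjusted, by simulation.** There were 4,000 replicates per cell (Monte Carlo SE of each power at most 0.8 point), with both analyses run on the same replicates. The adjusted analysis is a linear model for the binary outcome on arm and baseline IOP with HC2 standard errors. Ranges cover blocks of four or no blocks, and a site ICC of 0 or 0.10. The equivalent change in subjects is 1/(SE ratio)² − 1.

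| Correlation | Power change, 150 (points) | SE ratio, 150 | Half-width, 150 (points) | Equivalent subjects | Power change, 70 (points) |
|---|---|---|---|---|---|
| 0 | −0.6 to −0.1 | 1.004 | 17.0 | −1% | −0.9 to −0.4 |
| 0.2 | −0.1 to +1.2 | 0.991 | 16.7 | +2% | −0.1 to +0.4 |
| 0.35 | +2.3 to +3.5 | 0.964 | 16.3 | +8% | +1.3 to +1.8 |
| 0.5 | +6.6 to +7.6 | 0.918 | 15.5 | +19% | +3.3 to +4.7 |

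**6. Sensitivity (150 randomised, no blocks; correlations 0.2, 0.35, 0.5).**

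- Control mean 16 (72% vs 85%): +0.4, +1.7, +4.8 points.
- Control mean 20 (28% vs 47%): +0.4, +3.1, +5.7 points.
- Unequal sites (45 down to 4 subjects): +0.4, +3.1, +6.6 points.

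The form of the standard error does not produce the gain: an unadjusted linear model with HC2 errors is within 0.3 point of the plain test at 150. Logistic standardisation is within 1 point of the linear model throughout.

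**7. Error rates.** Under the null, the plain test rejects 4.7–5.6% of the time and the adjusted linear model 4.5–5.5%.

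**8. Cross-checks.** A separate simulation used 65 per arm, assumed rates of 40% vs 60%, and logistic standardisation. Relative efficiency was 0.99, 1.02, 1.05 and 1.18 at correlations 0, 0.2, 0.3 and 0.5. The last two are worth 65 × 1.05 = 68 and 65 × 1.18 = 77 per arm. Two repeats of step 5 with 64 per arm gave changes of −1.3 and −0.4 points at correlation 0, +0.2 and +1.0 at 0.2, +3.2 and +2.8 at 0.35, and +6.3 and +7.3 at 0.5.

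**9. Site terms (correlation 0.35).** Section 8.2 states: "Computer-generated randomization lists will be used, with separate randomization lists for each clinical site". Without blocks, adding nine sites to the baseline-adjusted model moved power from 62.8% to 60.1% and from 61.9% to 61.4% at 150, and from 33.1% to 29.4% and from 33.7% to 30.9% at 70. With blocks at 150 the moves were 64.0% to 63.3% and 62.9% to 64.2%. Three pooled groups cost 0.1 point at 150 with blocks, 0.4–0.6 without, and 1.0–1.2 at 70 without.

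**10. The 20% endpoint (150 randomised).** Adjustment moved power from 36.6% to 38.4%, 41.1% to 41.9% and 42.7% to 43.1% at correlations 0.2, 0.35 and 0.5.

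**The case against.** The strongest reply is that the plan contains no error. The test is valid, the endpoint is secondary, and no power is claimed for it. The benefit hangs on a correlation the documents do not supply, and at 0 to 0.2 it is practically nil. The entry range also makes the top value demanding. Under the assumed baseline distribution, truncation cuts the SD from 3.5 to about 2.75. If the relation is linear, 0.5 among enrolled eyes then implies about 0.59 before truncation. All of this stands. It limits the size of the point but does not remove it, because the downside is about a point of power.

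The public text is also incomplete: section 6.1 stops mid-sentence. The covariate can therefore be called unused only in the public text. Still, the sentence on secondary endpoints is whole and names its method.

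Setting aside the 20% endpoint may look inconsistent, since its gain at correlation 0.2 (+1.8 points) exceeds the gain for 5–18 mmHg there (at most +1.2). That is a fair observation. But the gain for the 20% endpoint shrinks as correlation rises, while the gain for 5–18 mmHg grows.

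Finally, section 8.6 lets the investigator withhold the 12-month washout for safety, and the public text does not say how those eyes count. The simulations assume random loss, so the gains may not carry over exactly. This affects both analyses and is a separate matter that baseline adjustment does not settle.

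**Conclusion.** The concern holds as an efficiency point on one secondary endpoint. The planned test is valid but sets aside a complete pre-randomisation covariate. With 150 randomised, the gain in power is nil at correlation 0, negligible at 0.2, about 2 to 3.5 points at 0.35 and about 7 points at 0.5. With 70 randomised, the gain is at most 4.7 points, from a plain power of only 32–34%. These figures rest on the assumed IOP distribution, effect size, random loss and correlation, none of which the documents give. The direction of the result does not depend on the responder rates tried. This is a worthwhile improvement, not a needed correction, and zero gain is a plausible outcome.

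**What to change.** For the 5–18 mmHg endpoint at 12 months, prespecify the between-arm risk difference with 95% CI, adjusted for baseline washed-out mean diurnal IOP. Either a linear model with robust standard errors or standardisation from a logistic model will do. Fix the choice before unmasking, and keep the plain test of proportions as a supporting analysis.

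Site need not be a required covariate. Add it only if the per-site lists are blocked, and then as a few pooled groups fixed in advance.

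The cost is one or two lines of analysis text and one degree of freedom, with no extra data or subjects. If baseline proves unrelated to 12-month IOP, the main simulation puts the loss at no more than 0.6 point of power with 150 randomised and 0.9 with 70; one repeat at 64 per arm gave 1.3. The risk difference with its interval also shows readers how large the difference between devices is, which a test alone does not.

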#### 6.2 Sample Size

The study size is based on the primary endpoint.

A power calculation yields a sample size of 65 subjects per arm for a 1:1 randomization ratio. Assuming a 15% loss to follow up at 12 months, a total of 75 randomized subjects are required per arm.

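### Site is a randomization stratum, but the visible analysis of the two secondary responder endpoints names no site stratification; a pooled test would be conservative if the site lists are balanced and responder rates differ materially between sites

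*Combined protocol and SAP*

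**What the plan says.** On allocation, Section 8.2 states: "Computer-generated randomization lists will be used, with separate randomization lists for each clinical site". It gives no block size or other balancing rule. The Study Outline sets the number of sites: "Up to eight clinical sites in Europe and one in South America". That is at most nine lists.

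Section 5.0 defines two binary secondary endpoints: "A reduction in IOP of at least 20% following the wash-out, as compared to the washed-out baseline", and "An IOP of no less than 5mmHg and no more than 18mmHg at 12 months post washout". The one visible sentence on how they are compared is in the Statistical Analysis row of the Study Outline: "Secondary endpoints will be evaluated using tests of proportion for subjects meeting the specified endpoints". It does not say whether sites are pooled or stratified.

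Section 6.2 bases the trial size on diurnal IOP, not on the responder endpoints: "The study size is based on the primary endpoint". The public text of Sections 6.1 and 6.2 is visibly cut short, so fuller analysis text may exist that is not shown.

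**The concern.** When arms are balanced within each site, differences in responder rate between sites cancel out of the treatment difference. A pooled two-proportion test leaves them in its variance. Its standard error is then larger than the true sampling variation, its type I error falls below nominal, and it loses power against a test stratified by site.

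Sites could plausibly differ. Section 7.1 admits three glaucoma diagnoses, Section 7.3 allows prior selective laser treatment, implantation is manual, and at Month 12 the investigator may judge washout inappropriate. The documents give no figure for the between-site spread.

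Pre-specification is also at stake. With the test unnamed, the choice between pooled and stratified analysis stays open until data are seen, and the two can disagree near the significance threshold.

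**Working it through.** **The plan's own figure.** Section 6.2: "A power calculation yields a sample size of 65 subjects per arm for a 1:1 randomization ratio", then "Assuming a 15% loss to follow up at 12 months, a total of 75 randomized subjects are required per arm". 65 × 1.15 = 74.75, rounded up to 75, which reproduces the figure. Dividing instead gives 65 / 0.85 = 76.5, or 77, within 2 per arm. The 65 cannot be rebuilt, because no alpha, power, effect or SD is shown. Nothing below changes it.

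**Inputs from the documents.** Up to nine sites; 65 evaluable per arm, so 130 / 9 ≈ 14 eyes per site; 1:1 allocation; separate site lists.

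**Assumed inputs.** Two-sided alpha 0.05, equal site sizes, blocks of 4 where lists are blocked, the responder rates and the between-site spread. None is a document figure.

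**Formulas.**
- Pooled test: z = (p1 − p0) / √[p̄(1 − p̄)(1/n1 + 1/n0)].
- Cochran-Mantel-Haenszel (CMH), over sites j with a_j responders in the test arm, t_j responders in all, and arm sizes m1j and m0j with n_j = m1j + m0j: z = Σ(a_j − m1j·t_j/n_j) / √Σ[m1j·m0j·t_j(n_j − t_j) / (n_j²(n_j − 1))].
- Pooled SE over true SE with balanced sites: 1/√[1 − s²/(p(1 − p))], where s is the between-site SD of the responder rate.

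**Step 1, analytic, p = 0.5.** If the pooled test has 80% power, stratified power is Φ[(1.96 + 0.8416) × SE ratio − 1.96], ignoring the small cost of stratifying.
- s = 0.05: 1/√0.99 = 1.005; power 80.4%.
- s = 0.10: 1/√0.96 = 1.021; power 81.6%.
- s = 0.15: 1/√0.91 = 1.048; power 83.6%.
- s = 0.20: 1/√0.84 = 1.091; power 86.4%.

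**Step 2, simulation with site spread on the probability scale.** 9 sites × 14 eyes = 126, 20,000 trials per cell. Power is at 0.40 vs 0.63; type I error and SE ratio are under the null. Gains (CMH minus pooled, in points) come from unrounded figures.

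| Site SD | Blocked: pooled SE / true SD | Blocked: pooled type I | Blocked: power, pooled vs CMH (gain) | Unblocked: pooled type I | Unblocked: power, pooled vs CMH (gain) |
|---|---|---|---|---|---|
| 0 | 1.00 | 5.0% | 74.5 vs 73.6 (−0.9) | 5.1% | 73.7 vs 70.8 (−2.8) |
| 0.05 | 1.00 | 5.0% | 74.2 vs 73.7 (−0.6) | 5.2% | 74.1 vs 71.1 (−3.1) |
| 0.10 | 1.01 | 4.9% | 74.7 vs 75.3 (+0.6) | 5.0% | 74.2 vs 72.8 (−1.4) |
| 0.15 | 1.04 | 4.0% | 75.7 vs 78.3 (+2.6) | 5.3% | 73.7 vs 74.9 (+1.3) |
| 0.20 | 1.08 | 3.5% | 76.2 vs 81.3 (+5.1) | 5.1% | 74.3 vs 79.0 (+4.7) |

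With unblocked lists the null SE ratio is 0.98 to 0.99 throughout, so the pooled error bars are not too wide at any spread.

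**Step 3, simulation with site spread on the logit scale.** Blocks of 4, 126 to 128 eyes, control success 50%, log odds ratio 1.03 (test success 1/(1 + e^−1.03) ≈ 74%). Ranges are across separate runs.

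| Logit SD | Pooled type I | Pooled power | CMH power | Gain |
|---|---|---|---|---|
| 0 | 5.0% | 79.9–80.0% | 79.3–79.7% | −0.6 to −0.3 |
| 0.5 | 4.4–4.6% | 75.5–75.9% | 76.3–77.2% | 0.6 to 1.3 |
| 0.75 | 4.0–4.4% | 71.6–71.9% | 74.4–74.9% | 2.8 to 3.0 |
| 1.0 | 3.1–3.7% | 65.5–66.3% | 71.1–71.5% | 5.1 to 6.0 |

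Up to a logit SD of 0.25 there is no gain. Logit SDs of 0.5, 0.75 and 1.0 correspond to probability SDs of about 0.12, 0.17 and 0.21, so Steps 2 and 3 agree.

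**The case against.** The strongest objection is that the plan may contain no mismatch at all. A reader might infer that it specifies an unstratified test. It does not: a CMH test is itself a test of proportions and would fit the sentence, and the statistics section is visibly cut. This stands. What can be said is that the visible text names no stratification, not that it chose a wrong method.

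A reader might also infer that the error bars are too wide in any case. That needs balance within each site list, and no blocking rule is documented. With unblocked lists the pooled test keeps its size and its standard error. This stands too, and is why the point is conditional.

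Nor is power lost whenever sites differ. Only differences in responder rate matter, and small ones produce no loss. Stratifying across nine small sites has its own cost when sites are alike.

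Finally, the larger losses need wide spreads. A logit SD of 1.0 around 50% puts 95% of sites between 1/(1 + e^1.96) ≈ 12% and 88% control success; an SD of 0.5 spans about 27% to 73%. No document figure supports any particular value.

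These objections limit the size and priority of the point. They leave standing that site is a documented stratum, that the visible analysis is silent on it, and that settling the matter in advance costs almost nothing.

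**Conclusion.** The point holds conditionally. If the responder comparison pools sites, the site lists are balanced and responder rates differ materially between sites, the pooled test is conservative: type I error falls to about 3 to 4% at the widest spread examined. The power lost is nil up to a logit site SD of 0.25, about 1 point at 0.5, 3 points at 0.75 and 5 to 6 points at 1.0. These sizes rest on assumed responder rates, alpha, block size, equal sites and between-site spread. If the lists are unblocked, only a possible efficiency gain remains, and it can be negative.

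A reader might take this as a threat to the trial's main conclusion or its size. The documents do not support that. Both endpoints are secondary, the sample size rests on diurnal IOP, and the error described does not inflate false positives. The analysis of the primary endpoint is not visible, so nothing is claimed about it. Priority is low to moderate.

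**What to change.** Unless the text not shown already does so:

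1. State in Section 8.2 whether each site list is blocked or otherwise balanced. Block sizes can be kept from the sites.
2. If the lists are blocked, state that both responder endpoints are compared with a CMH test stratified by randomizing site. Report the Mantel-Haenszel risk difference with its 95% CI.
3. Fix, before unmasking, a rule for pooling small sites or sites with evaluable subjects in only one arm. At about 14 evaluable eyes per site on average, some may be much smaller.
4. If the lists are not blocked, name the chosen test in advance and give the reason.

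The cost is a few sentences. Site is known for every subject, and no new data or patients are needed. The statistical downside is about 1 point of power or less if sites are alike and lists are blocked, and up to about 3 points if CMH is used with unblocked lists.
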